The current study proposes to interrogate these mechanisms and how they differ as a function of sex and age. We will first leverage our ongoing experimental study examining endotoxin-induced depression in older adults (R01AG051944, PI [name]) to test for sex differences in endotoxin-induced alterations in negative and positive affective processes among older adults. This study is expected to recruit 160 subjects aged 60-80 years (80 females vs. 80 males). We next propose to recruit an additional 40 healthy premenopausal women (age 30-40) to participate in this supplemental study, which will allow us a complementary test of age as a vulnerability factor for endotoxin-induced depression and associated affective responding mechanisms in females. Specifically, in this randomized placebo-controlled experimental study, we aim to:

1. Examine the effect of female sex on affective responses to endotoxin in older adults. We hypothesize that, compared to males, females will present with higher negative affective responses and lower positive affective responses to endotoxin.

2. Examine the effect of age on affective responses to endotoxin in females. We hypothesize that, compared to older females, younger females will present with higher negative affective responses and lower positive affective responses to endotoxin.

3. Examine the correlation between inflammatory response and affective response to endotoxin according to sex and age. We hypothesize that the correlations between circulating proinflammatory cytokines and affective responses following endotoxin administration will be stronger in older females than in older males and in younger females than in older females.

Exploratory Aim: Examine the prospective associations between acute affective responses to endotoxin and long-term development of depressive disorders over 2 years, extending our preliminary findings.

RESEARCH STRATEGY

A. SIGNIFICANCE

A.1. Female Sex: A Vulnerability Factor for Inflammation-Induced Depression?

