Methods: In a randomized, double-blind, placebo-controlled design, 115 participants (69 females, mean age 24.1 ± 6.3 years) received either low-dose endotoxin (0.8 ng/kg of body weight) or placebo (same volume of 0.9% saline). Blood sampling for IL-6 and TNF was obtained approximately every hour post-injection for the next six hours (T1-T6), along with assessment of social disconnection and depressed mood using the POMS. **Results:** Endotoxin (vs. placebo) led to significant increases in IL-6 ($P<0.001$) and TNF levels ($P<0.001$). Endotoxin (vs. placebo) also led to significantly greater increases in depressed mood ($P<0.001$), and these effects did not change when controlling for sickness symptoms ($P<0.05$) (Fig. 1). Additional analyses found that endotoxin induced increases in IL-6 and TNF which were similar between the two sexes, but suggested that women showed significantly greater increases in depressed mood than men in response to endotoxin ($P<0.05$). Similar results were found for feelings of social disconnection. **Conclusion:** Endotoxin induces increases in depressed mood, which are not due to sickness symptoms (i.e., headaches, muscle pain, shivering, nausea, breathing difficulties, and fatigue). Additional analyses suggested that women are more sensitive to an inflammatory challenge and show greater increases in depressed mood and social disconnection as compared to men. However, these analyses were limited to younger adults. Given the different hormonal milieu of younger vs. older women, and the regulation of inflammation by endocrine hormones, this study will evaluate inflammatory and affective responses in older adults stratified by sex and examine whether there are sex differences in inflammatory and affective responses.

C.1.1.2. Increases in inflammation correlate with depressive symptoms following endotoxin.

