Cognition and Executive Function. Behavioral tasks will be administered by computer to assess key aspects of executive function at baseline (Visit 1) and 3-hours post-injection during the experimental session.⁶³ The *Spatial 2-Back* task is used to assess Updating, the ability to monitor and replace information in working memory. The *Color-Shape* task is used to assess Shifting, or the ability to switch between mental sets. The *Antisaccade* task is used to assess Inhibition. Participants are tasked with inhibiting a reflexive response towards a visual cue in order to correctly identify a target stimulus presented elsewhere.

Emotion Regulation. Participants will complete questionnaires assessing dispositional and situational emotion regulation strategies and attitudes towards emotions. Participants will also complete a 20-30 minute standardized emotion regulation task⁴⁴. The task includes two phases: a reactivity phase and a regulation phase, and assesses the ability to down-regulate negative emotional response to negative images and/or film clips using reappraisal strategies. Participants receive instructions as to how to reappraise (e.g., thinking about the “silver lining” or imagining oneself at a distance from the negative emotion). The dependent variable is the degree to which self-reported emotion changes when reacting to versus reappraising negative stimuli. The task also includes assessment of the ability to up-regulate positive emotion using cognitive strategies (e.g., thinking about a positive image/film clip in such a way that more positive emotion is felt). The stimuli used in the emotion regulation task are drawn from standardized databases and have been used in many previous studies, including studies conducted in our group with younger breast cancer survivors.

Physical Sickness Symptoms (i.e., muscle pain, shivering, nausea, breathing, difficulties, and fatigue) will be assessed hourly by self-report, and controlled in analyses to ensure that the social or affective consequences of inflammatory challenge are not due simply to individuals feeling more ‘sick.’

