All measured variables will be assessed for distributional qualities and transformed if necessary for use in the selected statistical models. Adequacy of random assignment and matching will be tested using t-tests and chi-square tests as appropriate. All pre-classification variables (age, BMI, insomnia, medical comorbidity, prior depression history) and baseline values of outcomes will be compared; those that are significantly different between females and males (at $P < 0.15$) will be considered for inclusion as covariates in the main analyses. Missing data patterns will be analyzed to assess the potential for biased parameter estimates; missing data will not be imputed as the methods selected allow for missing data under common missingness assumptions. The basic design for Aim 1 is a 2 group (females vs. males) by 2 condition (endotoxin vs. placebo) independent balanced analysis of variance (ANOVA) with one or repeated outcome measures (times: T_{hr} where $hr = 0$ for baseline, 0.5 to 12 post-infusion; peak cytokine concentration at T_2)¹², conducted with linear mixed models (LMM). The number of repeated measures varies by assessment. The key results are the main effects of sex, condition, and their interaction; for those analyses with repeated measures, the two main effects and interaction will further interact with the time variable. Other planned analyses include lagged (time series) relationships between cytokine outcomes and affect measures via general linear modeling (GLM). Standard pharmacokinetic parameters (e.g., AUC, C_{MAX} , T_{MAX}) may also be used to create summary cytokine and affect profile outcomes. Finally, covariates (i.e., pre-classification variables such as prior depression history, insomnia, or baseline CRP) will be tested if appropriate (i.e., $p < 0.15$) to assess the robustness of the results and further explicate the findings. **Aim 1** is tested with LMM for the following outcomes (timepoints): POMS Depression, DACL, Social Disconnection (T_0 , $T_1 - T_{12}$), Observer rated depression (T_0 , $T_{2,4,6,8,12}$), Cyberball Social Exclusion Task (T_2), Emotion Tasks (T_0 , T_2), Social Support Questionnaire (T_0 , T_2), Social Choice Task (T_0 , T_2), Reward Response (T_0 , T_2), Reward Learning (T_0 , T_2), and Reward Motivation (T_0 , T_2). The basic design for **Aim 2** is identical to Aim 1 but using age as the group variable (young females vs. older females) instead of sex. **Aim 3** is restricted to the endotoxin condition to examine the correlations between inflammatory responses and affective responses to endotoxin according to sex and age. These correlations will be examined using mixed-effects model linear regression, and cytokines and depressed mood, including excess negative affect and deficits in positive affect, will be entered in the regression models in their longitudinal format, thus reflecting all the measurements performed during the study (T_0 , $T_1 - T_{12}$). **Exploratory Aim** is tested using mixed-effects logistic regression, separately in the endotoxin and placebo groups, because the outcome (depressive episodes) is a binary variable repeatedly measured over 2 years. The predictor variables include the sum of POMS depression during 12 hours of experimental session, Cyberball Social Exclusion Task (T_2), Emotion Tasks (T_2), Social Choice Task (T_2), and Reward Tasks (Response, Learning, Motivation, Sensitivity) (T_2).

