Endotoxin elicits sickness symptoms (e.g., nausea, achiness) that will be assessed as potential covariates in statistical analyses. The battery of administered tasks could lead to excessive fatigue and non-compliance. This is not currently a concern in the parent study, but we will monitor participants' subjective response to the tasks, as well as current fatigue, and assess these variables either as potential covariates or as indicators that the experimental session requires modification. While we do not anticipate strong emotional response to any of the tasks, there is the potential for carryover effects without task counterbalancing. However, since the order is the same for the experimental and the control group, such effects should not impact the primary research questions assessing group differences.

REFERENCES

1. Blazer DG. Depression in late life: review and commentary. *J Gerontol A Biol Sci Med Sci*. 2003;58(3):249-265.
2. Depression Guideline Panel: Clinical Practice Guideline 5: Depression in Primary Care, vol 2: Treatment of Major Depression. In: US Department of Health and Human Services PHS, Agency for Health Care Policy and Research, ed. Rockville, MD.1993.
7. Kuehner C. Gender differences in unipolar depression: an update of epidemiological findings and possible explanations. *Acta Psychiatr Scand*. 2003;108(3):163-174.

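### The documents disagree on whether the key results are adjusted for post-infusion sickness symptoms and fatigue; where they are, the estimate is no longer the total affective response to endotoxin

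*Combined protocol and SAP*

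**What the plan says.** Three sections bear on this point, and they differ.

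- **C.2.6, Physical Sickness Symptoms.** Muscle pain, shivering, nausea, breathing difficulties and fatigue are self-reported every hour "and controlled in analyses to ensure that the social or affective consequences of inflammatory challenge are not due simply to individuals feeling more" sick. This is a commitment, but it does not say which models it applies to.
- **C.3.** "Endotoxin elicits sickness symptoms (e.g., nausea, achiness) that will be assessed as potential covariates in statistical analyses". Staff will also monitor how participants react to the test battery, "as well as current fatigue, and assess these variables either as potential covariates or as indicators that the experimental session requires modification". This is an option, not a commitment.
- **C.2.8, Statistical Analyses.** "The key results are the main effects of sex, condition, and their interaction", with age replacing sex for Aim 2. On adjustment, "covariates (i.e., pre-classification variables such as prior depression history, insomnia, or baseline CRP) will be tested if appropriate". Sickness symptoms and fatigue are not mentioned.

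The Specific Aims state the target without reference to sickness. Aim 1 is to "Examine the effect of female sex on affective responses to endotoxin in older adults", and Aim 2 asks the same by age in females. No section defines a direct effect, a mediation method or an assumption under which one could be estimated.

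The preliminary study in C.1.1.1 reports an endotoxin effect on depressed mood at P<0.001. It then says "these effects did not change when controlling for sickness symptoms", with P<0.05, and concludes that the effect is not due to sickness.

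**The concern.** Sickness is measured after the infusion and, in the protocol's own words, is caused by endotoxin. Putting it in the model conditions a randomised contrast on one of its consequences. This has two effects.

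First, any part of the mood response that runs through feeling ill is taken out, so the result is no longer the response to endotoxin named in the aims.

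Second, what remains is not automatically the direct effect. Randomisation protects the comparison of endotoxin with placebo. It does not protect the relation between sickness and mood. Sickness and most of the mood scales are self-reported in the same session, so a general tendency to report negatively could raise both. Adjusting for sickness then induces an association between condition and that tendency.

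Covariate and outcome also overlap. The observer rating in C.2.6 includes somatic symptoms and retardation, while the covariate includes fatigue and muscle pain.

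At stake is how the key results are read. With the role of the covariate left open, an adjusted or an unadjusted endotoxin result could be put forward after the data are seen.

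**Working it through.** The plan gives no sickness effect size and no slope of mood on sickness, so there is no figure of its own to reproduce. The two P values in C.1.1.1 are thresholds without estimates or standard errors.

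**Inputs from the documents.** Endotoxin effect on depressed mood 0.51 SD in older females and 0.003 SD assumed in older males (C.2.9), so the interaction is 0.51 − 0.003 = 0.507. Within each sex, 20 receive endotoxin and 20 placebo (C.2.2).

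**Assumed inputs.** a = rise in sickness caused by endotoxin (SD). b = change in mood per SD of sickness. m and g = loadings of an unmeasured cause on sickness and on mood. Sickness and mood have within-arm SD 1.

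**Model.** Sickness = a·T + m·U + error. Mood = c·T + b·Sickness + g·U + error. The total effect is c + a·b. Regressing mood on condition T and sickness gives a sickness slope λ = b + m·g, so:

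- adjusted effect = total − a·(b + m·g)
- true direct effect = total − a·b

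**Female endotoxin effect (total 0.51)**

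| a | b | m, g | Adjusted | True direct |
|---|---|---|---|---|
| 1.0 | 0.3 | 0 | 0.51 − 1.0×0.30 = 0.21 | 0.21 |
| 1.5 | 0.3 | 0 | 0.51 − 1.5×0.30 = 0.06 | 0.06 |
| 1.5 | 0.2 | 0.4, 0.4 | 0.51 − 1.5×(0.20+0.16) = −0.03 | 0.21 |
| 1.0 | 0 | 0.4, 0.4 | 0.51 − 1.0×0.16 = 0.35 | 0.51 |
| 1.0 | 0 | 0 | 0.51 | 0.51 |

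Simulated trials of 20 v 20 agree with the formula to about 0.01. In rows 3 and 4 the adjusted figure is neither the total nor the direct effect. In row 4 sickness has no influence on mood at all, yet adjustment still lowers the estimate. In row 5 nothing changes.

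**Interaction (total 0.507).** With one sickness slope for both groups, adjusted interaction = 0.507 − (a_F − a_M)·λ.

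- Equal rise in both sexes: the bracket is 0 and the interaction stays at 0.507, with or without a shared cause.
- Rise 1.2 in females and 0.6 in males, λ = 0.2: 0.507 − 0.6×0.2 = 0.39.
- The same rises with a shared cause (m² = 0.5, g = 0.3, so λ = 0.2 + 0.212 = 0.412): 0.507 − 0.6×0.412 = 0.26.
- Rises reversed, λ = 0.412: 0.507 + 0.247 = 0.75.

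If the slope is fitted separately by group, the term removed is a_F·λ_F − a_M·λ_M, so a difference in slope alone also moves the interaction. With a = 1 in both and slopes of 0.3 and 0.1, it becomes 0.507 − 0.20 = 0.31.

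**Precision.** Sickness is correlated with condition, which multiplies the variance by 1 + a²/4, but it also explains some residual variance, which multiplies it by 1 − λ². At λ = 0.3 the net factor is 1.25×0.91 = 1.14 for a = 1.0 and 1.5625×0.91 = 1.42 for a = 1.5. Simulated trials run slightly higher (about 16% to 18%, and 46% to 52%) because the slope is estimated from 40 people.

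**The case against.** The strongest reply is that the main model is not shown to contain sickness. C.2.8 is the statistical section. It specifies group by condition (by time) and limits covariates to pre-classification variables, used to check robustness. C.3 speaks only of potential covariates. Only a measures paragraph in C.2.6 says the symptoms will be controlled, without saying where. This stands. A reader might infer that the plan's key estimates will be biased by this adjustment, but the documents do not establish that. They establish a conflict over whether it is made.

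The second reply is that the purpose is legitimate. Whether low mood is more than feeling ill is a fair question, and C.1.1.1 gives the unadjusted result first and the adjusted one beside it. This also stands, as a case for a labelled secondary analysis. It does not rescue the word ensure in C.2.6, because the adjusted coefficient answers the question only under an assumption that the plan never states.

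The third reply concerns evidence. A reader might take the move from P<0.001 to P<0.05 in C.1.1.1 as proof of attenuation. It is not: thresholds cannot separate a smaller effect from a less precise one. For the same reason they cannot support the statement that the effects did not change.

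Finally, a reader might infer that the interaction is bound to be distorted. It is not, as the working shows, and the documents report no sickness response by sex or age. Equality cannot be presumed either: C.2.2 notes greater fever in elderly than in young adults at a higher dose, and Aim 2 compares age groups.

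**Conclusion.** The concern holds as a conflict with consequences. C.2.6 commits to the adjustment, C.3 leaves it open, and C.2.8 omits it. If the C.2.6 rule is followed, the condition effect ceases to be the total affective response named in Aims 1 and 2, and it is a direct effect only if no unmeasured factor drives both sickness and mood.

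Under the assumed rises of 1.0 to 1.5 SD, slopes of 0.2 to 0.3 SD per SD, and presence or absence of a shared cause, the female estimate falls from 0.51 to between about 0.2 and 0. With no mediation and a modest shared cause it falls to 0.35. With neither, it does not move. All of these rest on inputs that the documents do not supply, so they show what the adjustment can do, not what it will do. Distortion of the sex or age interaction is conditional and can go either way (0.26 to 0.75 in the sex scenarios with unequal rises).

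This is more than a missing detail, because one stated rule, applied as written, gives a biased total effect. It falls short of a demonstrated error in the primary analysis. Should fix.

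**What to change.** Reconcile C.2.6, C.2.8 and C.3 before unblinding.

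- In C.2.8, state that the primary models for Aims 1 and 2, and the main Aim 3 model, exclude sickness symptoms and fatigue measured after the infusion. Pre-infusion (T0) values may be adjusted.
- Keep the sickness-adjusted model as a prespecified secondary analysis, labelled as mediation or sensitivity. State its assumption of no unmeasured common cause of sickness and mood, and report it beside the unadjusted estimate with confidence intervals.
- Report the sickness response by condition within each sex and age group, so that readers can judge whether the interaction could have been affected.
- Reword C.2.6 and C.3 to point to that secondary analysis. Monitoring fatigue to decide whether the session needs changing is a separate use and is unaffected.

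The cost is a few sentences and one labelled analysis, with no new data. The sponsor gives up the simple claim that an adjusted result shows the mood effect is not due to sickness.

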To examine whether transient increases in depressed mood during 6 hours following endotoxin administration predict subsequent depressive symptoms over a 2-year follow-up. *Methods*: In our ongoing study (K23AG049085, PI [name]), healthy older females aged 60-70 years who completed the above-described endotoxin protocol (N=22) were followed up for 21 months with an assessment of depressive symptoms every 3 months using the telephone-administered 9-item Patient Health Questionnaire (PHQ-9). **Results**: Endotoxin and placebo groups did not differ in subsequent depressive symptoms over 21 months ($P=0.37$), indicating that the intervention itself did not affect subsequent depressive symptoms (Fig. 2). In the endotoxin group, depressed mood assessed during 6 hours of experimental session at baseline strongly correlated with subsequent depressive symptoms over 21 months ($r = 0.71$, $P<0.0001$) (Fig. 3). However, in the placebo group, depressed mood assessed during 6 hours of experimental session did not correlate with subsequent depressive symptoms ($r = 0.07$, $P=0.74$). **Conclusion**: Transient increases in depressed mood following endotoxin administration strongly predict subsequent depressive symptoms over 2 years.

C.1.3. Increases in inflammation following influenza vaccine are associated with changes in reward processing. *Aim*:

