motivation and sensitivity for social reward),^{60,61} the Emotional Face Recognition task,⁶² and assessment of cognitive function.⁶³ At two hours post-injection only, participants will complete the Cyberball Social Exclusion task (i.e., self-reported sensitivity to social rejection).^{11,64} Proinflammatory cytokines levels will be repeatedly assessed through hourly blood draws, and measures of activation of the inflammatory transcription factor (NF- κ B) and inflammatory gene expression, as well as assessment of dopaminergic activity, will be obtained during the first half of the protocol prior to and immediately after peak cytokine responses. A between-subject parallel design will be used for the following reasons: 1) the proposed study involves endotoxin administration, and in a hypothetical crossover design, subjects who experience aversive sickness symptoms from endotoxin (possibly also from placebo due to expectation) might drop out, which would introduce bias and invalidate the results; 2) the effect of endotoxin on inflammation might not resolve between sessions; 3) repeated exposure to behavioral tests of social exclusion might alter responses; 4) two sessions have high subject burden; 5) distinct endotoxin and placebo groups are required for the 2-year follow-up.

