Experimental study session - Endotoxin vs. placebo administration: Similar to our previous research,⁸⁻¹² the experimental session will be conducted at the UCLA Clinical Translational Research Center (CTRC) using a randomized, double-blind, placebo controlled design. Before each session beginning at 8am, a CTRC nurse blind to the randomization schedule will assess height and weight as well as vital signs (blood pressure, pulse, temperature). Participants will be excluded if: (a) blood pressure less than 90/60 or greater than 160/120, (b) pulse less than 50 beats/minute, or (c) temperature greater than 99.5°F. An indwelling venous catheter with a heparin lock will be inserted into the participant's dominant forearm (right) for hourly blood draws and one into the non-dominant forearm (left) for a continuous saline flush (150 cc/h) for endotoxin vs. placebo administration. Baseline blood samples, self-report questionnaires, and experimental affective response tasks will then be completed. CTRC pharmacy will maintain the randomization assignment and prepare the endotoxin vs. placebo. After 90 minutes, participants will randomly receive either low-dose endotoxin (0.8 ng/kg of body weight) or placebo as an intravenous bolus over 30-60 seconds. NIH will provide reference endotoxin humans (*E. coli* group O:113).⁶⁸ Previous research has demonstrated the safe use of this reference endotoxin across many different samples^{41,68 57,58}. Throughout the study protocol lasting 12 hours, vital signs and blood sampling will be obtained every half hour for the first two hours, and then hourly. Placement of an intravenous catheter for this duration does not induce nonspecific increases in circulating levels of IL-6.⁹ Human Subjects section details safety monitoring. Although we are extending the protocol for 12 hours to accommodate a possible delayed termination of response in the older adult participants,^{57,58} subject burden precludes in person follow-up the next day; however, participants will receive a safety follow-up phone call 1 and 7 days after the CTRC session.

C.2.5. Baseline Measures: Prior to the Experimental Protocol

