Participants who complete the experimental session will be followed up by telephone over 2 years for the assessment of depressive symptoms and disorders. A research assistant will call participants every 3 months for administration of the PHQ-9. If their responses suggest depression (i.e., PHQ-9 ≥ 5), the project coordinator will conduct the SCID-5-RV over telephone. We have successfully conducted such a telephone follow-up in an ongoing depression prevention Study (R01AG026364, PI [name]). Telephone administration of the SCID has been found acceptable and comparable to in-person administration.^{101,102}

C.2.8. Statistical Analyses

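### The 2-year depression follow-up is limited to people who finish the 12-hour session, so anyone dosed who stops early is lost to the Exploratory Aim outcome

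*Combined protocol and SAP*

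**What the plan says.** - **Entry to follow-up (C.2.7).** "Participants who complete the experimental session will be followed up by telephone over 2 years for the assessment of depressive symptoms and disorders". The contact schedule is "A research assistant will call participants every 3 months for administration of the PHQ-9", with a telephone SCID-5-RV if the PHQ-9 is 5 or more.
- **Session (C.2.4).** The injection is a bolus given over 30 to 60 seconds. Observation then runs for half a day: "Throughout the study protocol lasting 12 hours, vital signs and blood sampling will be obtained every half hour for the first two hours", and hourly after that.
- **Safety contact (C.2.4).** This is a separate provision: "participants will receive a safety follow-up phone call 1 and 7 days after the CTRC session". It carries no completion condition. The same paragraph adds that "Human Subjects section details safety monitoring"; that section is not in the supplied text.
- **Analysis (C.2.8).** The Exploratory Aim uses mixed-effects logistic regression for repeated depressive episodes, fitted within each arm. The predictors are the POMS depression sum over 12 hours and several task scores at 2 hours. Missing data are not imputed. No rule is given for a session that ends early.
- **Drop-out (C.2.2).** In arguing against a crossover, the plan says that "subjects who experience aversive sickness symptoms from endotoxin (possibly also from placebo due to expectation) might drop out, which would introduce bias".
- **Preliminary data (C.1.2).** Among the women given endotoxin, "depressed mood assessed during 6 hours of experimental session at baseline strongly correlated with subsequent depressive symptoms over 21 months", with a reported correlation of 0.71. That sample was 22 older women who had themselves completed the protocol.

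**The concern.** A person who receives the bolus and leaves at hour 3 has had the full exposure. Under C.2.7 that person is never called for the 2-year outcome. Selection into follow-up therefore depends on a post-randomisation event that may be related to the reaction itself.

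The Exploratory Aim asks whether acute reaction predicts later depressive disorder. If early stoppers tend to be strong reactors, the upper end of the predictor is thinned out and some of the few expected episodes are never seen. The plan's reliance on methods that tolerate missing data does not help here: someone with no follow-up calls contributes no outcome rows, and the stated rule, not chance, put them outside the data.

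**Working it through.** The plan states no sample size, power or event rate for the 2-year aim, so there is no figure to reproduce. The calculation below only gives scale.

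**Inputs from the documents**
- Endotoxin arm: 40 older adults + 20 younger women = 60 (C.2.2).
- Correlation of session mood with later symptoms: 0.71 (C.1.2), used as an upper illustration. A value of 0.30 is an assumed lower one.
- Tolerability: no adverse events in over 170 people given this dose (C.2.2). This is not a count of early stops.

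**Assumptions**
- Early-stop rate q: 1%, 5% or 10%.
- Worst-case sorting: the stoppers are exactly the top fraction q of mood responders.
- Episode risk over 2 years: 10%, that is, 0.10 × 60 = 6 expected episodes in the endotoxin arm.
- Response X and depression liability Y are bivariate normal with correlation r.

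**How likely is any early stop?** P(at least one of 60) = 1 − (1 − q)^60, which is 45% at q = 1%, 95% at 5% and 99.8% at 10%. The expected numbers are 0.6, 3 and 6. For context, zero events in 170 gives a one-sided 95% upper bound of 1 − 0.05^(1/170) = 1.7% for adverse events.

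**Effect on the correlation.** Let a be the upper-q normal quantile and φ the normal density. With the top fraction removed, the mean of X is m = −φ(a)/(1 − q) and its variance is v = 1 − a·φ(a)/(1 − q) − m². The correlation becomes r′ = r√v / √(1 − r² + r²v).

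Example, q = 5%: a = 1.645 and φ(a) = 0.1031, so m = −0.1086 and v = 0.810. With r = 0.71, r² = 0.504, and r′ = 0.71 × 0.900 / √(0.496 + 0.408) = 0.67.

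**Effect on episodes.** The share unobserved is P(X > a and Y > b) / 0.10, with b = 1.282. The risk among those followed is 0.10 × (1 − share)/(1 − q).

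| r | q | r′ | episodes unobserved | of 6 expected | risk among those followed |
|---|---|---|---|---|---|
| 0.71 | 1% | 0.70 | 8% | 0.5 | 9.3% |
| 0.71 | 5% | 0.67 | 30% | 1.8 | 7.4% |
| 0.71 | 10% | 0.65 | 48% | 2.9 | 5.8% |
| 0.30 | 1% | 0.29 | 3% | 0.2 | 9.8% |
| 0.30 | 5% | 0.27 | 12% | 0.7 | 9.2% |
| 0.30 | 10% | 0.26 | 22% | 1.3 | 8.7% |

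**Weaker sorting.** If the tendency to stop correlates only 0.5 with mood response (assumed) and r = 0.71, then 5% to 10% stopping leaves r′ at about 0.70 and 14% to 24% of episodes unobserved, about half the worst case.

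**The case against.** The strongest case for leaving the text alone has four parts.

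1. **Early stopping may be rare.** The only tolerability data point that way: no adverse events in over 170 people at this dose, and none significant in 35 older women (C.1.1.3). This stands as a reason to doubt the 5% and 10% rows. It does not settle the matter, because adverse events are not early stops and the session has been lengthened from 6 to 12 hours (C.2.2).
2. **The aim is exploratory and fitted within each arm.** This stands. A reader might infer that the rule biases a comparison of later depression between endotoxin and placebo. The plan specifies no such comparison in C.2.8. The consequence is a restricted predictor range and lost episodes, which weaken an association.
3. **Stoppers need not be strong mood responders.** This also stands. People may stop for physical symptoms, and C.1.1.1 reports that the mood effect was not due to sickness symptoms. The C.2.2 remark that "subjects who experience aversive sickness symptoms from endotoxin (possibly also from placebo due to expectation) might drop out" concerns a hypothetical crossover. It shows that the plan's authors foresee reaction-related drop-out, not that it will happen within this session.
4. **The figure of 0.71 is fragile.** It comes from 22 people across both arms, from symptom scores and not diagnosed episodes, and from completers only.

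A reader might also infer that early stoppers are left without safety follow-up. The documents do not support that. The day-1 and day-7 calls go to participants without a completion condition, C.2.7 describes the 2-year calls as assessment of depression, and the section on safety monitoring is not available to check.

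**Conclusion.** The point holds in limited form. C.2.7 conditions the 2-year outcome on completing the session, nothing else in the documents brings early stoppers back, and the planned model cannot recover them. That early stopping is related to the strength of the reaction is plausible but not shown.

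The effect on the correlation is small even in the worst case. Lost episodes matter more, because only about 6 would be expected in the endotoxin arm under the assumed 10% risk. The upper figures (30% and 48%) need an unsourced 5% to 10% stop rate, perfect sorting of stoppers and r = 0.71 all at once, so they are bounds and not forecasts. With no early stops the loss is zero.

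The change is still worth making: it is cheap, and calls that were never made cannot be replaced at analysis.

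**What to change.** - **C.2.7.** Define the follow-up population as everyone who receives any part of the endotoxin or placebo injection, whether or not they finish the session. Record the time and reason of each early stop and report them by arm.
- **C.2.8, Exploratory Aim.** Keep the 12-hour POMS sum as planned. Beside it, add a sensitivity analysis that includes early stoppers through predictors measured at common times: the 2-hour tasks, and POMS over the hours observed in everyone, for example up to the 2-hour peak. Do not use a per-assessment average over unequal durations. Mood peaks at 2 hours (C.1.1.3, C.2.2), so an average cut off at hour 3 is mostly peak and not comparable with a completer's 12-hour value.
- **Parent-study participants.** The parent study's follow-up rule is not in these documents, and 74 of its participants had already completed all procedures by January 2019 (C.2.3). Apply the change where that study's follow-up allows, and report any early stoppers who were not followed.

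**Cost.** One revised sentence in C.2.7, a short addition to C.2.8, and 24 months / 3 months = 8 short calls per early stopper, plus a SCID where triggered, within a call schedule already planned. Those few people will have an incomplete 12-hour predictor, and anyone who stops before the 2-hour tasks will lack those scores too.
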